17.0 Provisions to Monitor the Data to Ensure the Safety of Subjects*

N/A There are minimal risks to subjects in this research project

18.0 Provisions to Protect the Privacy Interests of Subjects

18.1 Research participants are not ever required to meet with somebody whom they do not want to interact. If the participant would like a different interviewer, or a different person to facilitate the TARGET sessions if they are in the treatment group, then the research team will grant them that wish if possible. The participant will be informed at consent, and reminded throughout the study, that they can choose to stop any interview or intervention session at any time without any consequences or repercussions whatsoever. The participant has the option to not answer any questions that they find too personal and do not want to share with the interviewer. This information is all discussed with the participant during the informed consent process at the beginning of the study.

18.2 Research team members are trained in interviewing skills, including how to talk with the research participant in an empathic manner that helps put them at ease, which is particularly important considering the sensitive nature of some of the questions. Regarding the TARGET program for those in the treatment groups: all of the interventionist are trained counselors who are trained in working clinically with participants and have experience talking with our research participants in an empathic manner.

18.3 The only information the research team will access that does not come directly from the participants are the administrative data collected from department of corrections databases. This includes the following:

Commented [A3]: Are these all applicable?

- race/ethnicity
- release dates;
- type and length of supervision being released into;
- if you are on court mandated treatment during incarceration or post-release, and what type of treatment is required;
- custody levels at initial assignment and release;
- prison identification number;
- date of birth;
- both community and institutional (at time of entry into facility and final) risk scores, and which assessment tool is used;
- treatment and program participation;
- Protected Health Information from the Department of Corrections database;
- criminal history, including length of sentence, number of priors, age of first arrest, age at present offense, list of convictions, and what you are serving your current sentence on;
- recidivism data, including dates and number of: rearrests resulting in a 48 hour stay, jail time, incarceration for a new conviction, re-incarceration from state prison for a new offense or technical violation, residential sanction facility;
- technical violations, including what the violation was and the result of violation;
- sanctions, including type, number received and reason for sanction;
- education level at admission and at release;
- employment status on admission and for those on parole;
- home plan upon release and housing status for those already released;
- program treatment referral or receipt by parole, including your need, services received and services completed

19.0 Compensation for Research-Related Injury

19.1 N/A.

20.0 Economic Burden to Subjects

20.1 The only potential economic burdens include travel time and/or expense related to transportation to research site. However, the research team is mobile and usually conducts interviews in the participants' home community.

21.0 Consent Process

21.1 The consent process takes place in prison for eligible participants released to our participating counties in the study window. Research team members facilitate the consent process. Consent is obtained electronically with the tablets that store REDCap. The consents are discussed and obtained in person at the prison after the research team member introduces the project to the potential participant and explains why they have been selected. Potential research participants are given as much time as they need to make a decision on whether to participate in the research.

The research team is following the “SOP: Informed Consent Process for Research (HRP-090) for the consent process.

22.0 Process to Document Consent in Writing

22.1 The consent process takes place in prison for eligible participants released to our participating counties in the study window. Research team members facilitate the consent process. Consent is obtained electronically with the tablets that store REDCap. The consents are discussed and obtained in person at the prison after the research team member introduces the project to the potential participant and explains why they have been selected. Potential research participants are given as much time as they need to make a decision on whether to participate in the research.

The research team is following the “SOP: Informed Consent Process for Research (HRP-090) for the consent process.

24.0 Resources Available

24.1 Research team members will schedule in advance with the primary contact person the days to go to the prison for recruitment and baseline data collection. Each interview will last for between 1.5 and 2 hours and will take place in rooms where the conversation can be confidential.

24.2 Participants will be referred to mental health staff in the prisons if the research team member assesses they need counseling as a result of answering the questions on the interview packet. Specifically, the research team member will make a referral through the classification officer and/or primary contact person at the prison. Additionally, the informed consent contains resources for the participant if they are feeling emotional distress or need immediate assistance.

Title: Researching Resiliency in Stressful Experiences (RISE) Program for Men Leaving Incarceration

NCT #: NCT04785677

Date: 4/14/2020

Analytic Plan. STATA version 14 will be used for data cleaning, coding, and analysis.

Prior to analysis, data will be examined for missing and outlier values to resolve any issues.

Descriptive statistics will be computed for each variable. Correlation matrices and squared multiple correlations will be examined for multicollinearity and singularity. The reliability of scales composed of multiple items will be assessed. Precautions will be taken to minimize the amount of missing data (i.e., robust methods of participant tracking and incentives to participate). If missing data occurs, analyses will be undertaken to test for the assumption of missing at random (MAR) or missing completely at random (MCAR). Based on the determined pattern and proportion of the missing data, the recommended procedures for multiple imputation may be performed. Multivariate statistical methods must meet multiple assumptions before analyses can occur. We will test for the following assumptions: normality, multicollinearity, homoscedasticity, independence of error terms, and linearity. If assumptions are not met, appropriate corrections and transformations will be made.

Key Mechanisms of Change and Community Stability. We will use the multivariate statistical test of Analysis of Covariance (ANCOVA) to test our study aims around key mechanisms of change (i.e., trauma symptoms, coping, impulsivity, and aggression) and community stability (i.e., housing and employment). One two-level independent variable indicates the study condition: the comprehensive trauma-based reentry program condition and the TAU control condition. ANCOVA allows for an assessment of between-group differences on key mechanisms of change and community stability after controlling for the effects of one or more covariates (e.g., race, other program participation, criminal history). The purpose of this analysis is to partial-out the effects of study condition on key mechanisms of change and community stability, determining whether any effects are due to the covariates and/or are a result of the study condition assignment.

Power analysis. To determine the sample size, we conducted an a priori power analysis with the software program G*Power. We conducted the power analysis to make sure we would be able to detect differential effects on key mechanisms of change and community stability between participants allocated into the two study conditions. We powered the study based on conducting multivariate analysis using ANCOVA. We used a small effect size estimate - Cohen's d of .15 - based on guidance and data from the Clinician Administered PTSD Scale on a similar population.⁶⁷ Being able to detect small effects is important as we may find minimal difference between group members. Using an alpha of .05 and powered at a .80 level across two groups with up to seven covariates, a sample of 352 would allow us to detect small effects. Thus, a targeted sample size of 400 provides statistical power greater than .80, giving us strong confidence that we will be able to detect even small difference between study conditions.

Recidivism. Survival analysis will be conducted to analyze time-to-event on recidivism outcomes (i.e., time to arrest and time to incarceration). Participants without the occurrence of the events will be censored at their last known event-free time point. Survival curves will be constructed using Kaplan-Meier estimates. Using the Kaplan-Meier curve allows us to derive the median, or that time at which 50% of cases of the event of interest has occurred, and the mean (i.e. the average time it took for the event to occur). Although there are several methods available to analyze time-to-event curves, the proposed study uses a Cox proportional hazard model which is a regression method for survival data and has been used in previous criminal justice-related studies. The Cox model allows for the identification of differences in survival rate due to study condition and prognostic factors, such as covariates. Further, the Cox model provides an estimate of the hazard ratio and its confidence interval. There are two underlying assumptions of the Cox proportional hazard model: (1) the hazard ratios of two people are independent of time and (2)

are valid only for time independent covariates. For the current study, results will be displayed for comparison of survival distributions for three years post-release.

Power Analysis. The Bureau of Justice Statistics (BJS) 2005-2014 data show that 76.5% of prisoners age 24 or younger released in 2005 were arrested within three years of release. Specifically, 51.8% were arrested within the first year, an additional 17% in the second year, and an additional 7.7% in the third year. Our goal is to reduce recidivism by 28% over three years. Using these data and the method described by Collett (2003, pp. 299-312), we calculate that the hazard ratio of recidivism for this study at 1.39, meaning that members of the control group will recidivate 39% faster than participants receiving the targeted treatment. Using the same BJS data, we calculated the median survival time (pre-recidivism) for members of the control group at 17.28 months. The median survival time suggests that 50% of the control group will recidivate by 17.28 months after release from incarceration. These data provided the basis for the power calculation. The power analysis was conducted using PS software.⁷⁸ Results show that for a study with 200 experimental participants and 200 control participants, a hazard ratio of recidivism of 1.39, and a median survival time for the control group of 17.28 months, we will be able to reject the null hypothesis that the treated and control survival curves are equal with a probability (power) of .810. The Type I error probability associated with this test of this null hypothesis is 0.05. Therefore, the study will have adequate statistical power.

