4.0 Study Intervention

4.1 The comprehensive trauma-based reentry program has two primary components: a trauma-based intervention paired with community stabilization reentry efforts. Consistent with evidence-based reentry approaches,⁶⁶ the proposed intervention will use trauma-trained reentry practitioners to deliver the intervention and provide reentry supports including coordinating substance abuse treatment, assisting with housing, and providing employment services.

Trauma-Based Intervention Component. Trauma Affect Regulation: Guide for Education and Therapy (TARGET) is a manualized, cognitive-behavioral, trauma-based group program designed for both young men and young women with a history of LTEs who are experiencing trauma symptoms. TARGET has an established evidence base.⁶⁷⁻⁷¹ Up to fourteen TARGET sessions will be paired with the specialized reentry supports. Up to four sessions will occur prior to release and up to ten sessions will be delivered in the community post-release.

TARGET helps participants understand and manage trauma memories and affective dysregulation and provides psychoeducation and skills-based learning on how to process and manage trauma-related reactions to stressful life situations, including PTSD symptoms, traumatic grief, and shame. The goal of TARGET is to increase emotional regulation and coping, helping participants gain control of intense emotions and posttraumatic stress reactions while simultaneously solving daily stressors and maintaining sobriety. Like other present-focused, cognitive-behavioral interventions, TARGET provides a systematic approach to processing trauma that does not require memory processing or risk re-traumatization. The comprehensive trauma-based reentry program pairs trauma-based components with community stabilization reentry efforts. Consistent with evidence-based reentry approaches, the proposed intervention will use trauma trained reentry specialists to deliver the intervention and provide reentry supports to help improve community stabilization.

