5.0 Procedures Involved*

6.1 The proposed 5-year study is a two-armed 1:1 Randomized Controlled Trial (RCT) implementing and evaluating the effectiveness of a comprehensive trauma-based reentry program for young men releasing from prison to the community evaluated as moderate- to high- risk for recidivism. A total of 400 18-35 year old males releasing to one of the four participating urban and rural counties in Florida (Columbia, Duval, Leon, and Suwanee) will be randomly assigned to participate in the comprehensive trauma-based reentry program or a treatment-as-usual (TAU) control group. Participants in the comprehensive trauma-based reentry program will participate in up to four group sessions while incarcerated and up to 15 group sessions in the community after release. The effectiveness of the comprehensive trauma-based reentry program for 18-35 year old males will be evaluated on the following constructs: key mechanisms of change, community stability, and recidivism. Participants assigned to the treatment-as-usual control group will remain eligible to participate in all reentry services they normally would have received.

The purpose of this study is to evaluate the impact of a comprehensive trauma-based reentry program for moderate- to high-risk young incarcerated males between the ages of 18-35 on post-release outcomes. We will assess changes in key mechanisms of change (i.e. mediators) as well as post-release outcomes. The key mechanisms of change include: trauma symptoms (PTSD, depression, anxiety, and substance abuse), coping, impulsivity, and aggression. Post-release outcomes include community stability (i.e., housing and employment), and recidivism (i.e., re-arrest and re-incarceration for technical violation or new crime; time to re-incarceration).

5.2 Research team members are trained interventionists in order to assess if there are adverse behaviors or thoughts during service delivery (treatment group) and during data collection interviews (all participants). All interviews are conducted one-on-one so the research team member can assess for adverse reaction to the data collection or treatment delivery.

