16.0 Data Management* and Confidentiality

16.1 Data analysis will include statistical techniques such as t-tests, correlations, chi-square testing, ANOVA, survival analysis, structural equation modeling, and multilevel modeling.

16.2 To minimize risk of accidental disclosure of identifiable private information, a meaningless code number will be established for all participants immediately following consent. That code number will be attached to all interview tools rather than identifying information. A separate document linking identifying information and meaningless ID numbers will be stored apart from consent forms in a locked cabinet in the research team office.

16.3 Research team members are all trained on using REDCap to store, encrypt, and protect the data. REDCap servers are housed in a local data center at Florida State University and all web-based information transmission is encrypted. REDCap was developed specifically around HIPPA-Security guidelines. All identifiable information is replaced with a meaningless code number for the sake of confidentiality.

The researchers will obtain the participants department of corrections' identification nm

16.4 Data collectors all have tablets with REDCap. They collect information from the participants on their tablets using REDCap, which is housed in a local data center at FSU. We will maintain all study records, including signed and dated consent documents for six years after completion of the study.

16.5 Data will be stored in REDCap for six years after completion of the study. Research team members have access to the data and are responsible for receipt or transmission of the data..

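### Only the program arm meets in trial-run groups, but the RQ1/RQ2 ANCOVA and its sample size name no clustering; the effect depends on a group size and ICC that are not given

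*SAP*

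**What the plan says.** Protocol section 4.0 describes TARGET as a "manualized, cognitive-behavioral, trauma-based group program". Section 5.0 (paragraph numbered 6.1) has program men attend "up to four group sessions while incarcerated and up to 15 group sessions in the community after release". Control men keep the reentry services they would normally receive. Section 15.1 mentions 12-step groups among department services for both arms, but the trial does not run those.

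For RQ1 and RQ2 the SAP (Key Mechanisms of Change and Community Stability) specifies ANCOVA: "One two-level independent variable indicates the study condition: the comprehensive trauma-based reentry program condition and the TAU control condition". The example covariates are race, other program participation and criminal history. There is no group, facilitator or site term.

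The SAP's first power paragraph says that "across two groups with up to seven covariates, a sample of 352 would allow us to detect small effects" and that "a targeted sample size of 400 provides statistical power greater than .80". It mentions no group size, ICC or design effect.

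Two statements bear on clustering. The SAP will test "independence of error terms, and linearity. If assumptions are not met, appropriate corrections and transformations will be made". Protocol section 16.1 ends its list of techniques with "structural equation modeling, and multilevel modeling". Neither names a cluster unit, an outcome or an arm.

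**The concern.** Men who share sessions and a facilitator may end up with more similar outcomes than men who do not. Here that can arise from trial delivery in one arm only. If it does, and the ANCOVA treats all men as independent, the standard error of the condition effect is too small and the stated power is too high.

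The plan leaves room to respond, but does not say by which unit independence will be checked or which correction follows. The choice would then be made after the data are seen. The documents also list no group or facilitator identifier among the data. Without one, neither a check by group nor a multilevel model could be run.

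**Working it through.** **Reproducing the plan's figure.** Inputs from the SAP: two groups, seven covariates, alpha .05, power .80. ANCOVA power comes from a noncentral F with df 1 and N - 9 and noncentrality f²N.

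- f = .15, N = 352: .0225 × 352 = 7.92, power .801 (the smallest N reaching .80 is 351).
- f = .15, N = 400: .0225 × 400 = 9.00, power .849.
- The SAP labels the effect d = .15. For two equal groups f = d/2 = .075, so the noncentrality at 400 is .005625 × 400 = 2.25 and power is .322.

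So 352 matches f = .15 (d = .30), with no allowance for clustering.

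**Adding clustering in the program arm.** Group size m and ICC are assumptions, since the documents give neither. With all 400 men analysed and equal total variance in the arms:

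- Program-arm design effect: DE = 1 + (m - 1) × ICC. Control arm: 1.
- Variance inflation at 1:1: V = (1 + DE)/2.
- Power at 400: noncentrality 9.00/V.
- Type I error of an analysis ignoring groups, if group effects are real but average zero: 2[1 - Φ(1.96/√V)].

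Example, m = 10 and ICC .05: DE = 1.45, V = 1.225, noncentrality 9.00/1.225 = 7.35, power .772. Type I error is 2[1 - Φ(1.771)] = .077.

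Power equals .80 at V = 1.141, that is DE = 1.282, so the threshold ICC is .282/(m - 1).

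| m | Threshold ICC | Power at ICC .02 / .05 / .10 | Type I error ignoring groups, ICC .02 / .05 / .10 |
|---|---|---|---|
| 4 | .094 | .839 / .823 / .797 | .053 / .059 / .068 |
| 5 | .071 | .835 / .814 / .780 | .055 / .062 / .074 |
| 6 | .056 | .832 / .806 / .763 | .056 / .065 / .080 |
| 8 | .040 | .825 / .788 / .731 | .058 / .071 / .092 |
| 10 | .031 | .818 / .772 / .700 | .060 / .077 / .104 |
| 12 | .026 | .811 / .755 / .671 | .063 / .083 / .115 |

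At d = .15 the same inflation takes power from .32 to between .31 and .26 for ICC .02 to .05.

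**Simulation checks** (continuous outcome, about 200 men per arm, groups of 8 to 12, group effects averaging zero):

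- A .05-level F test for group differences detects ICC .02 with probability .13-.16, ICC .05 with .34-.41 and ICC .10 with .69-.76.
- Testing by group and correcting only if significant gives type I error .055-.061.
- Always allowing for program groups, with controls as singletons and Satterthwaite degrees of freedom, gives .050-.051.
- The SAP states that "STATA version 14 will be used for data cleaning, coding, and analysis". The usual cluster correction there, which counts the 200 control singletons as clusters, gives .055-.061.
- Dichotomous outcomes (assumed prevalence .2 to .5) give .058-.118 uncorrected, and .046-.049 with a cluster-robust log risk ratio and Satterthwaite degrees of freedom.

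**County.** Both arms release to the same four counties. In a simulation with groups of 10 nested in counties, no group effect and county ICC .02 or .05, a program-group test without county has type I error of about .04 or .03. Adding county in both arms restores about .05.

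**The case against.** The case against has several parts.

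- **Size.** It rests on two assumed inputs. About 200 program men enrol over eighteen months (section 8.2) from several prisons to four counties, so small groups cannot be ruled out. With 4 to 6 men per group, power at ICC .05 stays at .823 to .806. A reader might infer that the .80 claim fails at an ICC of about .03 to .04. That fits only groups of about 8 to 10.
- **Persistence.** Attendance is up to a maximum, men move from prison to community groups, and section 18.1 lets a man ask for another facilitator. If only half the program men were effectively grouped (an assumption), power at ICC .05 would be .819, .810 and .801 for groups of 8, 10 and 12. The tabled figures are near an upper bound on harm. The manualised format may also reduce differences between groups.
- **Existing provision.** A reader might infer that the planned ANCOVA is invalid. The documents do not support that. If the program does nothing, type I error stays at .05. If the independence check is run by group and acted on, it is about .055 to .061 for groups of 8 to 12. The gap is an unnamed unit and method.
- **Identifiers.** A reader might infer that group membership will not be recorded. Sections 6.1 (data banking) and 18.3 cover interview and administrative data and do not claim to list delivery records. A roster may well exist.
- **Priority.** The claim of power above .80 already fails at the stated d = .15, without clustering.

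These points limit the size and certainty of the problem. They do not supply a named cluster unit, a method or a power statement that allows for groups.

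**Conclusion.** The point holds in a conditional form. Trial-run groups exist in one arm only, the RQ1/RQ2 model has condition as its single factor, and 352 and the power at 400 assume independent men. Whether this matters in practice depends on a group size and an ICC that the documents do not give.

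At ICC .02 the claim of power above .80 survives for every group size from 4 to 12, if the effect is read as f = .15 and all 400 men are analysed. At ICC .05 it survives for groups of 4 to 6 and fails for 8 or more. At ICC .10 it fails throughout, only just for groups of 4. Any excess type I error requires group effects that are real but average zero.

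This is worth changing because a valid standard error can be fixed in advance cheaply. It ranks below the effect-size error. Confidence is medium, since outcome correlation within groups is unknown.

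**What to change.** 1. Keep each program man's prison group, community group and facilitator in the analysis data set, and state whether groups are fixed or open.
2. Prespecify for RQ1 and RQ2 an analysis with clustering in the program arm only, controls as singletons, and one named primary cluster variable. Include county of release as a covariate in both arms, so that county differences are not read as group variation. For continuous scores, use a partially nested mixed model with small-sample degrees of freedom, or cluster-robust standard errors with a correction based on the number of program groups. For dichotomous outcomes (MINI disorders, binary housing and employment items), use a logistic or modified Poisson version with the same clustering.
3. When the power paragraph is corrected for the effect size, restate power over a stated range of group size, including small groups, and ICC.

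No change to the Cox model is asked for here.

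The cost is SAP wording, modest record-keeping, slightly wider intervals and a lower stated power. If there is no clustering, the loss is about .01 of power: at d = .30, simulated power goes from .849 to .843, .848 to .839 and .852 to .841 for groups of 8, 10 and 12 (without the county term).

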1.0 Objectives*

1.1 The purpose of this study is to evaluate the impact of a comprehensive trauma-based reentry program for moderate- to high-risk young incarcerated males between the ages of 18-35 on post-release outcomes. We will assess changes in key mechanisms of change (i.e. mediators) as well as post-release outcomes. The key mechanisms of change include: trauma symptoms (PTSD, depression, anxiety, and substance abuse), coping, impulsivity, and aggression. Post-release outcomes include community stability (i.e., housing and employment), and recidivism (i.e., re-arrest and re-incarceration for technical violation or new crime; time to re-incarceration).

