9.0 Subject Population*

Commented [A1]: Eligibility : Age, Risk Factor Identification (spectrum?), Screening for Lifetime Traumatic Experiences, Conversational English, Cognitive Consent, Release to Leon or Duval

Random Number generator (randomization)

9.1 Participant inclusion requirements include: (1) male; (2) age 18-35; (3) identified as having risk for recidivism; (4) screened as experiencing at least one LTE; (4) releasing from incarceration to one of our four study counties within six months; (5) conversational English; and (6) being able to cognitively consent into study participation.

9.2 Participants may be excluded if: they (1) identify as women; (2) younger than 18 or older than 35; (3) no demonstrated any risk; (4) not cognitively able to understand what it entails to be a research participant.

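### The primary-objective ANCOVA does not name each outcome's baseline score as a covariate, and gives no time window for other program participation

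*SAP*

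**What the plan says.** The SAP section on key mechanisms of change and community stability compares the arms by ANCOVA "after controlling for the effects of one or more covariates (e.g., race, other program participation, criminal history"). The first power analysis assumes a model "across two groups with up to seven covariates", without naming them. The stated purpose of the adjustment includes "determining whether any effects are due to the covariates and/or are a result of the study condition assignment".

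Neither document names the baseline score of an outcome as an ANCOVA covariate. Two protocol statements point towards its use. Section 1.1 says "We will assess changes in key mechanisms of change (i.e. mediators) as well as post-release outcomes", and section 16.1 lists "structural equation modeling, and multilevel modeling" among possible techniques.

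The data exist. Items 6.4 and 6.5 (printed under protocol section 5.0) place a baseline interview in prison straight after consent, and measure PTSD, depression, anxiety, substance use, coping, impulsivity and aggression at every interview. Housing is measured only after release. The baseline employment items refer to the period before the current incarceration.

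Neither document says which period other program participation covers.

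**The concern.** There are two separate issues.

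**Baseline score.** In a trial that measures the same scale before and after treatment, the baseline value is usually the strongest single predictor of the follow-up value. An ANCOVA without it discards precision already paid for in data collection. The SAP itself says that detecting small effects matters here.

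**Undated covariate.** Adjusting for something fixed before randomisation leaves the treatment comparison intact. Adjusting for something that assignment can change does not: part of the effect may be removed, or a spurious difference introduced. Other program participation could be either kind.

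Behind both lies the open list. With only examples and a ceiling of seven, the covariates for the primary objective could be chosen after outcomes are seen.

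**Working it through.** **1. The plan's own figure.** SAP inputs: alpha .05, power .80, two groups, up to seven covariates, effect size .15. Method: noncentral F with 1 and N − 2 − 7 degrees of freedom and noncentrality N·f².

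- With .15 entered as Cohen's f, N = 351, or 352 in equal arms, which matches the SAP. Power is .801 at 352 and .849 at 400.
- With .15 as Cohen's d, as the SAP labels it, f = .075 and N = 1398. That mismatch is a separate matter.
- With zero, one or seven covariates, N is 351 each time. The calculation counts covariates only as lost degrees of freedom and takes no credit for variance they explain.

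**2. What the baseline score would add.** Smallest detectable difference in SD units, 1:1 allocation, two-sided .05, 80% power:

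(1.960 + .842) × √[4(1 − r²)/N]

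Here r is the baseline-outcome correlation. The documents give no value, so .3 to .7 is an assumption. The row for 300 analysed is likewise an assumption (25% loss).

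| Analysed | r = 0 | r = .3 | r = .5 | r = .7 |
|---|---|---|---|---|
| 400 | .280 | .267 | .243 | .200 |
| 300 | .323 | .309 | .280 | .231 |
| ratio √(1 − r²) | 1 | .954 | .866 | .714 |

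Example: 2.802 × √(4/400) = .280, and .280 × .866 = .243. The exact noncentral-F value for 400 and r = 0 is .281.

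The r = 0 column is a model whose covariates explain no variance. If race or criminal history already predicts outcome, the starting value is lower and the gain smaller. The figures are approximate for depression, anxiety and substance use, which come from Yes/No MINI items. Correlations may be low because baseline is taken in prison and follow-up in the community.

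**3. What other program participation could mean.**

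- *Before enrolment.* The other two examples, race and criminal history, are attributes fixed before enrolment and are drawn from corrections records (item 6.5). Section 18.3 lists treatment and program participation without dates. On this reading the covariate is valid.
- *After randomisation.* Section 18.3 also lists services received and completed under parole. Section 4.1 has the program's practitioners coordinate substance abuse treatment and help with housing and employment, so later service use could differ by arm. That is an inference: no text says that services arranged by the program count as other programs.

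**4. Why no size can be given for the second reading.** For a symptom score, adjusted benefit = total benefit + β(p₁ − p₀). Here p₁ and p₀ are the shares using services in the program and control arms, and β is the pooled within-arm slope of symptoms on use. Equal use gives no change.

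Illustration, all inputs assumed: 60% against 50% use, direct benefit .20 SD, service benefit .30 SD. Total benefit = .20 + .30 × .10 = .23.

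- Use unrelated to severity: β = −.30; adjusted .23 − .030 = .200, 13% lost.
- Less severe men use more services: β = −.658; adjusted .23 − .066 = .164, 29% lost.
- More severe men use more services: β = +.267; adjusted .23 + .027 = .257, 12% gained.

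Even the sign depends on inputs that the documents do not supply. These figures show that the direction is open; they do not estimate a bias.

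**The case against.** **The harmless reading of program participation is at least as natural.** This stands. Race and criminal history are pre-enrolment attributes, and the list of measures contains no service-use measure. The section 18.3 list that includes parole services carries a margin comment asking whether all its items apply. A reader might infer that the SAP plans to adjust for post-randomisation services. The documents do not say so; they only fail to exclude it.

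**Baseline may be intended anyway.** Assessing change and listing multilevel modelling both point that way, and an open list does not forbid it. True, but neither statement puts baseline into the ANCOVA.

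**Omitting baseline is not an error of validity.** This stands for complete data. A reader might go further and infer bias from follow-up loss that depends on baseline. That needs a complete-case analysis, which the SAP does not select: it will examine the missing-data pattern and says "the recommended procedures for multiple imputation may be performed".

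**The order of baseline and randomisation.** A reader might infer that baseline could follow assignment, because section 5.0 says only that men "will be randomly assigned to participate in the comprehensive trauma-based reentry program or a treatment-as-usual (TAU) control group" and section 9.0 has only a margin note, "Random Number generator (randomization"). But item 6.4 puts the interview immediately after consent, and section 14.1 says the consent form explains the chances of being in the control group. Baseline first is the natural reading. It needs confirming; it is not a defect.

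**Conclusion.** The point holds as a gap in specification that should be fixed, with moderate confidence. It is not a planned error.

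The firm part is precision. Adding each outcome's own baseline score would lower the detectable difference by about 5%, 13% or 29% (1 − .954, .866, .714) at assumed correlations of .3, .5 or .7, against a model whose covariates explain nothing. The true gain depends on correlations that the documents do not give and on what the listed covariates already explain.

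The conditional part is the undated covariate. Harm requires that it means later services, that those services count as other programs, and that their use differs by arm. None of the three is established. If all three held, the adjusted comparison would no longer be the effect of assignment, with direction and size unknown.

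**What to change.** In the SAP section on key mechanisms of change and community stability:

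- **(a)** Include the baseline value of each mechanism outcome as a covariate in that outcome's model. This takes one of the seven covariates allowed and one degree of freedom.
- **(b)** Name the covariates in advance and restrict them to values fixed before randomisation. Limit other program participation to that period, or omit it if the records cannot be dated. Analyse later service use as exploratory only.
- **(c)** For housing, which has no baseline measure, use other pre-randomisation covariates. Pre-incarceration employment can serve for the employment outcome.
- **(d)** Confirm, and then state, that the baseline interview precedes assignment.

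The cost is SAP wording plus two checks: whether program records carry dates, and the order of baseline and assignment. No new data are needed. The downside is that any service-adjusted estimate becomes exploratory. Neither (a) nor (b) replaces the other: in the illustration where use is unrelated to severity, a baseline severity score would leave the 13% loss unchanged.
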